#### 1644 **4.8.2. Participant Selection**

- 1645 See Section 4. for eligibility criteria.
- 1646

1649

1650

- **4.8.3. Data Elements**
- 1648 Recipient Post-transplant:
  - 1. Recipient Baseline Immunosuppression & Rejection
  - 2. Rejection Episodes & Treatment
- 1651 3. Liver biopsy

1652 Liver biopsy is required in all patients who are diagnosed with acute and/or persistent

- rejection. The biopsy will be obtained prior to or within 24 hours after treatment for rejection.
- 1655

#### 1656

#### 4.8.4. Sample Size and Power Calculations

1657

Power analyses are based on the proportion of organs that have experienced at least one rejection episode in the first year after transplant, with LDLT and DDLT compared using a test of binomial proportions. We assume 360 LDLT and 355 DDLT patients, two-sided testing and a significance level of 0.05. We will have 93% power to detect a difference between the LDLT and DDLT proportions of 13% (e.g., 43% versus 56%), and will have even greater power if the same 13% difference is closer to zero or one.

1664 **4.8.5. Statistical Analysis** 

1665 The goal of this specific aim is to find predictors of organ rejection, and in particular to 1666 see if rejection rates differ between LDLT and DDLT. We will first use Cox regression, 1667 comparing time from transplant to organ rejection in each group. We will adjust for 1668 patient demographics, recipient and donor ABO and HLA typing, and whether the donor 1669 is related to the recipient. To test the effect of liver regeneration on organ rejection, we

- 1670 will include clinical and biochemical indicators of regeneration in the model.
- 1671 Radiological and pathological correlates, and extent of organ damage will also be tested.
- 1672 We will also consider frequency of rejection in cases of recurrent rejection. If there are
- 1673 enough cases of recurrent rejection, we will compare LDLT with DDLT using a multiple
- 1674 event Cox regression. Severity of rejection in LDLT versus DDLT will also be
- 1675 considered, restricted only to cases with rejection.

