202 203 204 205 206 207 208 209	
 
Primary Objective
 
1. To measure hepatic function and mass in living donors at enrollment, intraoperatively, and following hepatectomy, in order to determine whether return of hepatic function following donation correlates with rate of liver volume regeneration, biochemical impairment, and clinical events, and to see whether return of function is complete by 3 months post-resection.
 

210 211 212 213 214 215 216 217 218 219	
 
Secondary Objectives         
 
To correlate liver function in donors with long-term health outcomes and the incidence of clinical complications.
 
To correlate success or failure of regeneration with a series of selected clinical and laboratory variables in donors and recipients.
 
To collect liver biopsy and serum samples prospectively from a large series of donors and recipients which may form the basis for subsequent characterization of protein and gene expression of selected inflammatory and growth-related molecules.
 
 
 

220 221	3.8. Secondary Aim 4: To evaluate differences in the immune response to LDLT vs. DDLT grafts.
222 223 224 225 226 227	
 
Primary objectives
 
1. To determine whether LDLT, which is associated with a regenerating liver, meaningfully increases the incidence of clinical rejection. In the cohort, we will compare the incidence of immunologic complications, specifically the incidence and severity of rejection between LDLT and DDLT in a defined set
 

-	Deviced Calcert Protocol 02100(

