## 4.8. Secondary Aim 4: To evaluate differences in the immune response to LDLT vs. DDLT grafts.

1566

Living donor liver transplantation presents a unique immunological setting that is determined by three major variables that are different from the DDLT setting, with the potential to impact on short and long-term graft and patient survival, as well as recurrent disease:

- Regeneration may be associated with different pattern of lymphocyte trafficking in and out of the graft resulting in a differential repopulation of the liver with donor cells, and unknown effects on the extent of peripheral chimerism.
- Transplantation of a lobe from a living donor is done under conditions allowing extremely short cold ischemic time (60 vs. 500 minutes), a variable that may affect the severity of the inflammatory and immune response.
  - 3. We assume that 40% of LDLT are done between genetically related individuals, resulting in a potentially more favorable HLA matching.
- 1578 1579

1577

1580 Preliminary data demonstrate a potentially different alloimmune and antigen-specific 1581 immune response in recipients undergoing LDLT. Previous single center studies have suggested a reduced rate of rejection after adult-to-adult LDLT. Interestingly, there is a 1582 trend toward more rapid recurrence of hepatitis C infection, a phenomenon that may be 1583 1584 related to liver regeneration and/or inhibition of immune related anti-HCV response. The 1585 prospective cohort study will be designed to address whether LDLT affects mechanistic 1586 issues of liver transplantation immunobiology. The clinical findings will be correlated 1587 with specific laboratory assays, and will be compared with a control group undergoing 1588 DDLT transplantation. These findings will determine the opportunities for appropriate 1589 clinical modifications in the immunosuppression protocol, aiming at better outcomes for 1590 graft rejection and reduced frequency of recurrent disease. The clinical data and the 1591 specimens that are collected will be used to further support hypothesis-driven 1592 investigations, aiming to determine patterns of immune response and the potential 1593 development of favorable induction of tolerance, and those that are aiming to reduce the 1594 recurrence of the primary liver disease.

1595

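### The rejection Cox model in 4.8.5 adjusts for donor relatedness, which varies essentially only within LDLT, so its LDLT coefficient compares unrelated LDLT with DDLT rather than LDLT overall with DDLT.

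*Protocol*

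**What the plan says.** The first primary objective of Secondary Aim 4 (Protocol section 3.8) is an overall contrast: "To determine whether LDLT, which is associated with a regenerating liver, meaningfully increases the incidence of clinical rejection". Section 4.8.5 gives the goal as finding predictors of rejection, and in particular to "see if rejection rates differ between LDLT and DDLT. We will first use Cox regression".

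Section 4.8.5 then fixes the adjustment set: "patient demographics, recipient and donor ABO and HLA typing, and whether the donor", continuing "is related to the recipient. To test the effect of liver regeneration on organ rejection, we" and, on the next line, "will include clinical and biochemical indicators of regeneration in the model". It names no LDLT versus DDLT model without these terms and does not say which fit supplies the LDLT estimate for the objective.

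The introduction to section 4.8 names three features that set LDLT apart from DDLT: regeneration, short cold ischemia, and relatedness with the better HLA matching it may bring. On the third it says "We assume that 40% of LDLT are done between genetically related individuals". It gives no corresponding share for DDLT.

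The power statement in section 4.8.4 concerns the proportion with at least one rejection episode in the first year, compared by a test of two binomial proportions: "We assume 360 LDLT and 355 DDLT patients", two-sided, significance level 0.05, 93% power for 43% versus 56%.

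Section 4.2.5 (Primary Aim 2) separately plans a Cox comparison of time to rejection between LDLT and DDLT. It is adjusted for prognostic variables that are not listed.

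**The concern.** A covariate removes confounding when it varies in both groups. A related deceased donor would be exceptional, so relatedness has almost no counterpart among DDLT recipients. Putting it in the model does not balance the groups. It divides the LDLT group, moves the related part into another coefficient, and leaves the coefficient labelled LDLT describing unrelated LDLT only.

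A reader would naturally take that coefficient as the answer to the section 3.8 objective. If rejection differs between related and unrelated LDLT, the answer would be wrong for LDLT as it is actually performed: a real overall difference could be reported as none, or one of different size. If rejection does not differ between them, the estimate stays on target but loses precision, and section 4.8.4 no longer describes its power.

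**Working it through.** **Inputs.** From section 4.8.4: 360 LDLT, 355 DDLT, 43% versus 56%, two-sided 0.05, stated power 93%. From section 4.8: 40% of LDLT related. Assumed, because the protocol gives no figure: 0% of DDLT related.

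**1. The plan's own figure.** Two-proportion test with pooled null variance; power = Φ[(d − 1.96·SE₀)/SE₁], with d = 0.13.
- Pooled proportion = (360×0.43 + 355×0.56)/715 = 353.6/715 = 0.4945.
- SE₀ = √[0.4945×0.5055×(1/360 + 1/355)] = 0.0374.
- SE₁ = √[0.43×0.57/360 + 0.56×0.44/355] = 0.0371.
- Power = Φ(1.53) = 93.7%.

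The unpooled, continuity-corrected and arcsine forms give 93.9%, 92.7% and 93.7%. The stated 93% reproduces.

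**2. What the adjusted coefficient estimates.** Write the log hazard as β₁·LDLT + β₂·related + other terms. With no related DDLT, the log hazard ratios against DDLT are:
- unrelated LDLT: β₁
- related LDLT: β₁ + β₂
- average over the assumed LDLT mix: about β₁ + 0.4·β₂

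The coefficient on LDLT is β₁. It equals the overall effect only if β₂ = 0.

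**3. If related and unrelated LDLT differ (assumed effects).** Take HR 0.70 for related and 1.00 for unrelated LDLT, each against DDLT. The overall effect is about exp(0.4 × ln 0.70) = 0.87, while the LDLT coefficient is 1.00. A simulation (300 runs, one-year follow-up, 56% rejection in DDLT, 40% of LDLT related) with a larger assumed effect, log HR −0.7 in related LDLT only, gave a mean HR of 0.77 without the relatedness term and 1.00 with it. The null was rejected in 69% and 6% of runs.

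**4. If they do not differ.** The estimate is unchanged but rests on unrelated LDLT: 0.60 × 360 = 216 against 355.
- Pooled proportion = (216×0.43 + 355×0.56)/571 = 291.68/571 = 0.5108.
- SE₀ = 0.0431; SE₁ = 0.0428.
- Power = Φ(1.06) = 85.6%.

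If 30% of LDLT are related (252 unrelated), power is 88.6%; if 50% (180 unrelated), 81.3%. The variance inflation of the LDLT coefficient at 40% is 1.33. In the Cox simulation with a uniform HR of 0.68, power fell from 94% to 88% when relatedness was added.

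Steps 3 and 4 are alternative situations and do not hold together. Step 2 holds in both.

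**The case against.** **Another model exists.** Section 4.2.5 already plans an LDLT versus DDLT Cox model for time to rejection and names no relatedness or regeneration term. This stands: the protocol as a whole can answer the overall question, and it would be wrong to infer that it cannot. But the 4.2.5 covariates are unnamed, and 4.8.5, which carries the rejection objective, fixes a different set without pointing back.

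**The overall effect can be recovered.** Related LDLT versus DDLT, and a weighted average, are linear combinations from the same fit. This is true and no data are lost. But 4.8.5 does not ask for the combination, and the coefficient that would be reported by default is the narrower one.

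**The adjustment may be deliberate.** Relatedness could lower rejection through better HLA matching and so hide a harmful effect of the regenerating graft; finding predictors is also a stated goal. Both are fair reasons for an explanatory model. Neither makes that coefficient the answer to whether LDLT "meaningfully increases the incidence of clinical rejection".

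**Regeneration.** A reader might infer that post-transplant regeneration markers are planned as fixed covariates in the main model, so that values recorded after a rejection would predict it. The text does not establish this. The sentence has its own purpose and can be read as a second step, and it does not say how the markers enter. Nor does the month-3 liver imaging support the inference: the indicators placed in the model are clinical and biochemical, and radiological correlates come in a later sentence. What remains is a caveat. If the LDLT effect were read from a fit containing a marker on the causal path, it would be removed: in a simulation with the whole effect assumed to act through such a marker, HR 1.45 became 0.99.

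**Conclusion.** The point holds for relatedness. In the 4.8.5 model as written, the LDLT coefficient is unrelated LDLT versus DDLT. This follows from the model's form and does not depend on any assumed effect size. It rests on one assumption, that practically no DDLT donor is related to the recipient.

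How far that coefficient lies from the overall effect depends on the related-versus-unrelated difference, which the protocol does not give; HR 0.87 against 1.00 is an illustration. If there is no such difference, the cost is power alone: about 86% instead of about 94% at 40% related, and 81% to 89% for 50% to 30% related.

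A reader might infer that the 93% in section 4.8.4 is miscalculated. It is not; it is correct for the unadjusted overall contrast it describes. The matter is one of analysis wording in a secondary aim, worth correcting because the correction is cheap and makes the 4.8.5 estimate answer its own question.

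**What to change.** In section 4.8.5:

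1. State that the LDLT versus DDLT rejection effect is taken from a Cox model adjusted for pre-transplant recipient factors, without relatedness or post-transplant regeneration terms, and make it consistent with the rejection comparison in section 4.2.5.
2. Add a second model with three groups: related LDLT, unrelated LDLT and DDLT.
3. Label the HLA and regeneration fits as separate explanatory models from which the overall LDLT effect is not read. Enter any post-transplant regeneration marker as a time-dependent value measured before the rejection event.

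The power statement in section 4.8.4 can stay, since it describes the overall contrast. The cost is a few sentences and one extra model; no new data are needed.

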# 4.9. Secondary Aim 5: To establish a robust data and sample repository on liver transplantation that will be used to study clinical and biological questions as new technologies and resources become available.

- 1679 **4.9.1. Study Methods**
- 1680

1681 The NIDDK Central Repositories are three separate contract-funded components that 1682 work together to store data and samples from significant NIDDK-funded studies. One 1683 component is the Biosample Repository, which will gather, store and distribute biological 1684 samples from studies. The second component is the Genetics Repository, which will receive and process blood samples to allow genetic analyses. The Genetics Repository 1685 1686 will create immortalized cell lines or cryopreserve nucleated cells for future 1687 immortalization, and prepare DNA from one or both of these sources. The third 1688 component is a Database Repository that will gather, store and distribute the incremental 1689 or finished datasets from studies.

1690

1691 The NIDDK conducts and supports much of the clinical research on the diseases of 1692 internal medicine and related subspecialty fields. Many of the large clinical studies 1693 funded by the NIDDK collect biospecimens from subjects for analysis and store the 1694 samples for future study in a study-specific repository. The samples from the A2ALL 1695 Cohort Study will be collected over several years from carefully chosen subjects and are 1696 present in a finite quantity. Each sample is unique and cannot be replaced if lost, 1697 damaged, or contaminated. Therefore, it is essential that the samples be stored under 1698 optimal conditions, which vary from sample type to sample type. To this end, the NIDDK 1699 has established a Biosample Repository.

1700

Discovery of disease related genes requires a population of individuals with the genetic
variant, as well as a population of control (unaffected) individuals. Thus, a repository of
DNA samples, immortalized cell lines, and accompanying clinical and pedigree data is
clearly an invaluable resource for the research community studying liver disease and
issues relating to transplant such as regeneration, immunology, HCC and HCV. The
NIDDK has established a Genetics Repository for DNA samples for the study of the
impact of genetics on disease.

1708

In addition to the Biosample and Genetics Repositories, the NIDDK has established a
Data Repository that will store, maintain, perform quality control assessments, and
distribute data related to the studies storing materials at the Biosample and Genetics
Repositories. The Data Repository will foster the development of highly usable public
data sets, thus allowing re-analysis of these data and, where relevant, of specific
biosamples, thus optimizing use of study data and samples.

1715

The collection of patient and control biosamples and DNA samples from this and other studies for storage in the Biosample, Genetics and Data Repositories has the potential to become a resource with which researchers can rapidly validate clinical hypotheses and algorithms for clinical decision. The collections will also advance the development of

- 1720 prognostics, markers, and therapeutics. To date, no such collection has been available to
- 1721 the investigators interested in studying liver disease and transplant issues. The

1722 repositories will allow storage, maintenance, and quality control, and equitable, ethical

1723 distribution of biosamples and other resources important to the study of liver transplant.

1724 This will allow sharing of resources, thus encouraging work by junior investigators,

- investigators with novel approaches, and others not included in current collaborations,
- 1726 without excluding those who are established in their fields. In addition, the Genetics
- Repository may increase the sample size and the resulting power of a study to identifygenetic determinants of a disease. It will ensure that research participants will be making
- a maximal contribution, and will decrease duplicative sampling efforts. A2ALL is
- 1729 a maximal control on and will decrease duplicative sampling crioits. AZALL is 1730 committed to sharing the resources collected in this study with current and future
- 1731 researchers via the use of the NIDDK repositories.
- 1732

## 1733 **4.9.2.** Participant Selection

All eligible Cohort Study subjects will be presented with information and approached for
consent to have their biosamples, genetic material and non-identified data stored in the
NIDDK repositories for future study.

**4.9.3. Data Elements** 

## 1738 Sample Repository and Genetics Repository

- 1739 Specimen collection:
- 1740 Collection of blood and tissue for immediate and/or future analysis of mechanistic issues
- in LDLT immunobiology will be done as part of the cohort study, but will requireseparate consent form(s), some of which will be developed in an investigator initiated
- 1743 hypothesis-driven studies.
- 1744

1745 The following is a preliminary recommendation for collection of blood and tissue from

1746 LDLT and DDLT recipients and donors at specific intervals prior and after

transplantation. Some of the fresh specimens will be used for assays, whereas other willbe stored:

1749

## 1750 **Pre-transplant, Intraoperative and Post-operative**

1751

Donor and recipient whole blood for genetic repository (24 ml collected at enrollment forrecipients and on the day of donation surgery for the donor)

- 1754 Donor and recipient blood for biorepository (15 ml drawn at enrollment, day of surgery
- and post-transplant day 1, weeks 1 and 2\*, months 1, 3, 6\*, 12 and yearly through month
- 1756 60). Those subjects who have joined the study later in their transplant/donation
- 1757 experience may have blood drawn for the repository at annual visits from Year 5 through
- 1758 Year 10. However, because they will have entered the study after some collection
- timepoints, the total amount of blood drawn from these subjects will be similar to or lessthan that drawn from subjects who entered the study at the time of donor evaluation.
- 1761
- \*Donors will not have blood drawn at week 2 or month 6. Total blood drawn during the
- 1763 five-year study will be 219 ml for donors and a maximum of 304 ml for recipients.
- 1764
- 1765

1766 Additional collection of blood and tissue will be coordinated with other ancillary studies,

1767 and correlated with liver function tests. Revised Cohort Protocol 031006

#### 1768 **5. Human Subjects**

#### 1769 **5.1. Protection of Human Subjects**

1770 **5.1.1. Institutional Review Board** 

This study and analysis will be performed under Institutional Review Board (IRB)
oversight. Prior to the initiation of the study, an IRB approval for study of human
subjects will be obtained separately from the IRB of each of the participating transplant
centers and the DCC. Revisions to the study protocol and changes in the study design
will also be submitted to the individual IRBs for approval prior to implementation.

1776

Patients will be enrolled in the cohort study with full informed consent which will include
the gathering of privileged health information (PHI), the collection of blood and tissue
specimens beyond that normally performed for transplant clinical care, and the collection
of medical and quality of life information at defined intervals prior to and after the
transplant in donors and recipients.

- 1782
- 1783 **5.1.2.** Patient Confidentiality

1784 Special procedures for ensuring patient confidentiality will be implemented. Data 1785 transmission and the distributed data systems have multiple layers of security as 1786 discussed below in the study management section. Each study subject will be assigned an 1787 identification number. Only this number will be used to identify subjects in any 1788 individual tabulation. The PHI that is collected will represent the minimal necessary to 1789 successfully execute the study. Since this study plans to establish a link to the Scientific 1790 Registry of Transplant Recipients (SRTR) database, to reduce the data burden on the 1791 study coordinators, SRTR PX-ID numbers will be collected. The PX-ID does not include 1792 PHI. The only PHI that will be entered into the electronic data system is date of birth. It 1793 is expected that only group data will be published. If individual subject data are to be 1794 published, no identifying information will be included. The study files will be maintained 1795 in a secure location as described above. Access to computerized data will be restricted to 1796 study personnel. Password authorization will be enforced. Previous use of this security 1797 system and secured server indicates that this technique is very successful in assuring the 1798 protection of confidential information.

1799

Authorized representatives of the Sponsor, the National Institute of Diabetes, Digestive
and Kidney Diseases (NIDDK), National Institute of Health (NIH), participating clinical
institution, DCC monitoring staff, as well as the IRB, have access to medical records and
records from participation in this study. Such access is necessary to ensure the accuracy
of the findings.

1805 **5.1.3.** Risks to the Patient

Patients enrolled in this study will experience more than the normal amount of testing
which is customary for this complicated medical and surgical procedure. Additional time
will be required both before and after the transplant for the gathering of medical and
quality of life information. Blood will be collected and stored for special tests which are

not normally performed for this procedure. During and after the surgery liver biopsieswill be collected which add a small risk of bleeding.

